## **Selection and Withdrawal of Subjects:**

Inclusion criteria: All individuals diagnosed with Atrial Fibrillation and choosing to undergo a rhythm control strategy at Robert Packer Hospital with a BMI  $\geq$  27 will be eligible for the study. All subjects must be able to understand and willing to sign a written informed consent document.

Exclusion criteria: Individuals who are already taking metformin or other antidiabetic medications including insulin, have a diagnosis of diabetes, have a known allergy or FDA-labeled contraindication to taking metformin, eGFR below 30 mL/min per 1.73 m^2 or other clinical diagnosis of advanced renal disease,, have acute or chronic metabolic acidosis (serum bicarbonate <22 mEq/L), have a history of significant alcohol use (>2 drinks/day on average), have a history of hepatic dysfunction (serum bilirubin 1.5X greater than the upper limit of normal), have a history of New York Heart Association (NYHA) Class III or IV heart failure, or are pregnant will be excluded from the trial.

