#### **Trial Design:**

The proposed study will be a randomized control trial comparing metformin therapy to a control group in patients with a BMI  $\geq$ 27 and atrial fibrillation who have elected to undergo a rhythm control strategy with ablation. Upstream therapy with Metformin will be used in a randomized fashion. The only variation to the standard of care will be the addition of Metformin therapy and additional blood draws for safety monitoring and EKGs for measuring outcomes in both the intervention and control groups.

Patients meeting the below inclusion and exclusion criteria who provide informed consent will be randomized to control versus metformin therapy six weeks prior to rhythm control.

At baseline all study patients will be assessed for:

Age, Gender, Weight, BMI, Tobacco Use, Hypertension, Hemoglobin A1c, Hyperlipidemia, serum CRP, glomerular filtration rate estimating equation (eGFR), B12, liver function tests (AST, ALT, ALP, bilirubin, albumin, INR), lactic acid, History of Coronary Artery Disease by MI, PCI, or CABG, History of Valvular Disease, History of Obstructive Sleep Apnea, Type of AF and duration, Number of Antiarrhythmic Medications (not including beta-blockers or calcium channel blockers).

In addition, patients will fill out a survey to determine their Atrial Fibrillation Severity Score (AFSS) - a validated tool to assess the symptomatic burden of AF - and will receive education on dietary changes and exercise

Metformin will be initiated at 500 mg daily and increased as tolerated to 2000 mg daily over a three week period. Subjects will be instructed to hold Metformin on the day of any procedure or study requiring the administration of intravenous contrast and to resume 48 hours after the contrast administration and reinstituted only after renal function has been reevaluated and found to be at the patient's baseline. All patients will receive information on dietary changes to promote weight loss and will be encouraged to increase exercise activities. Patients will discontinue treatment at any time they are found to meet the baseline exclusion criteria for the study.

The initiation of the drug and the dosage increases will be overseen by a designee (mid-level cardiology practitioner) who will be responsible for stopping dosage increases if side effects occur. Six weeks after the initiation of drug the patient will undergo ablation with the intent of achieving rhythm control.

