# **Method of Assigning Subject Identification:**

The study design is a randomized control trial. After the subject's initial eligibility is established and informed consent has been obtained, the subject will be enrolled into the study by obtaining a randomly assigned subject number. The subject number will determine the randomization to the treatment or control arm

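### Diabetes is excluded by known diagnosis or drug use only, although HbA1c is measured at baseline, so the trial's own test can turn a randomised patient into a withdrawal

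*Combined protocol and SAP*

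**What the plan says.** All references are to the combined protocol and SAP.

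- **Selection and Withdrawal of Subjects** excludes "Individuals who are already taking metformin or other antidiabetic medications including insulin, have a diagnosis of diabetes". No HbA1c or glucose value appears. Two other exclusions do rest on a laboratory value: "eGFR below 30 mL/min per 1.73" (per m²) and "have a history of hepatic dysfunction (serum bilirubin 1.5X greater than the upper limit of normal".
- **Trial Design** and **Treatment of Subjects** both put HbA1c, eGFR and bilirubin on the baseline list for all study patients. HbA1c is repeated at the first rhythm-control attempt and at 3 and 6 months.
- **Trial Design** restricts allocation to eligible patients: "Patients meeting the below inclusion and exclusion criteria who provide informed consent will be randomized to control versus metformin therapy". It also says: "Patients will discontinue treatment at any time they are found to meet the baseline exclusion criteria for the study".
- **Method of Assigning Subject Identification** gives the sequence: "After the subject's initial eligibility is established and informed consent has been obtained, the subject will be enrolled into the study". It adds: "The subject number will determine the randomization to the treatment or control arm". Enrolment and allocation are thus a single act.
- **Assessment of Safety** has the exclusion criteria rechecked at each follow-up, and a patient found to meet one is withdrawn from the study.
- **Outcomes and Assessment of Efficacy** specifies intention to treat for the primary outcome and lists HbA1c as a secondary outcome.

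**The concern.** The trial measures the marker that could reveal undiagnosed diabetes but does not use it at entry. The information then acts after randomisation, where it does more damage. A metformin patient diagnosed from the baseline HbA1c stops the drug and leaves the study. A control patient so diagnosed leaves the study, or is prescribed an antidiabetic drug that may be metformin itself. No placebo is described, so a control patient's clinician would know that the patient is not taking metformin.

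Three things are at stake: outcome data lost from an analysis meant to include everyone randomised, dilution of the treatment contrast, and the HbA1c secondary outcome, which undiagnosed diabetes affects directly. There is also a route to imbalance between arms. HbA1c is repeated during follow-up, and Potential Benefits states that metformin slows progression from prediabetes to diabetes. New diagnoses, and so withdrawals, could then be more frequent in the control arm.

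**Working it through.** **1. Following an undiagnosed patient through the text.**

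| Step | Section | Result |
|---|---|---|
| No diagnosis, no antidiabetic drug | Selection and Withdrawal of Subjects | Not excluded |
| Consent, then random number | Method of Assigning Subject Identification | Arm assigned |
| Baseline HbA1c leads to a diagnosis | Trial Design; Treatment of Subjects | Now meets an exclusion |
| Exclusion met | Trial Design | Treatment stops |
| Exclusion met | Assessment of Safety | Withdrawn from the study |
| Primary analysis | Outcomes and Assessment of Efficacy | Intention to treat, so the outcome is still needed |

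No HbA1c value excludes anyone in itself. It matters only through a new diagnosis. This is a missing criterion, and seeing the result sooner would not cure it without a threshold.

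**2. Order of results and allocation.** The term *initial eligibility* is not defined, and no section says that the eGFR and bilirubin results must be in hand before the number is issued. Against that, Trial Design allocates only patients who meet the criteria, and Treatment of Subjects describes the baseline assessment before randomisation. The order is not stated, but the text leans towards results first.

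**3. The plan's own sample size.** Inputs from Statistics: control recurrence 30%; 30% fewer with metformin, so 0.30 × 0.70 = 21%; two-sided α = 0.05; 80% power; 3% attrition; 400 per arm.

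Pooled formula, with p̄ = 0.255 and d = 0.09:

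n = [1.96·√(2·p̄·(1−p̄)) + 0.8416·√(p₁(1−p₁)+p₂(1−p₂))]² / d² = [1.96·√0.37995 + 0.8416·√0.3759]² / 0.0081 ≈ 367 per arm.

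With continuity correction, n′ = (n/4)·[1+√(1+4/(n·d))]² = 389. Then 389/0.97 = 401.03, or 402 rounded up, so the stated 400 is reproduced to within 3%. Without the correction, 367/0.97 gives 379.

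**4. How many patients.** The documents give no rate of undiagnosed diabetes in this population, so 2–5% is an assumption. 800 × 0.02 = 16 and 800 × 0.05 = 40, or 8–20 per arm. For scale, the attrition allowance is 800 × 0.03 = 24. These are patients in a position to be diagnosed; fewer would be diagnosed, and fewer still withdrawn.

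**5. Effect on power.** Power = Φ[(d − 1.96·SE₀)/SE₁], with SE₀ = √(2·p̄·(1−p̄)/n) and SE₁ = √((p₁(1−p₁)+p₂(1−p₂))/n), no continuity correction. The baseline case is n = 400 × 0.97 = 388 per arm. Let x be the assumed share affected.

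- *Lost from the analysis:* n = 400 × (1 − 0.03 − x).
- *Kept, with no drug effect:* n = 388 and metformin-arm rate 0.21(1−x) + 0.30x.

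| x | Lost: n per arm | Lost: power | Kept: metformin-arm rate | Kept: power |
|---|---|---|---|---|
| 0 | 388 | 82.1% | 21.00% | 82.1% |
| 2% | 380 | 81.4% | 21.18% | 80.5% |
| 5% | 368 | 80.1% | 21.45% | 77.9% |

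Both scenarios treat every undiagnosed patient as affected, which overstates the effect. Neither models metformin use in the control arm, which would add dilution.

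**The case against.** The strongest reply is that the plan chose to exclude known diabetes, that this is a legitimate choice of target population, and that the effect on power is small. Harm also needs a chain of events: a diabetic-range result, a diagnosis, and then a stop or a new prescription. All of this is fair. But the plan's own rules turn a new diagnosis into a stop and a withdrawal, so it does not in fact keep undiagnosed patients in its population once they are identified. It removes them after randomisation instead of before.

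A reader might also infer that the random number is issued straight after consent, so that patients whose eGFR or bilirubin excludes them are randomised before the result is known. The documents do not support that. Eligibility must be established as well as consent, allocation is limited to patients meeting the criteria, and baseline assessment is described first. Assessment of Safety also has baseline renal and hepatic results reviewed, with immediate reporting of raised creatinine or bilirubin, though it does not time this against allocation. The study-flow figure was not readable in the text available and may show the order. What stands is an undefined term that leaves the possibility open.

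Nor do the documents support reading the baseline HbA1c as an existing exclusion that is merely checked too late: there is no threshold to check. Finally, comparison with the 3% attrition allowance gives scale only, since under intention to treat not every affected patient is lost.

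**Conclusion.** The point holds for diabetes. As written, the plan admits patients with undiagnosed diabetes, measures the marker that can identify them, and then removes those diagnosed after randomisation. That withdrawal conflicts with the intention-to-treat analysis, and metformin use by control patients becomes possible. For eGFR and bilirubin the point is limited to an ambiguity that needs clarifying; the documents do not establish that allocation precedes the results.

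The size is modest and rests on an assumed 2–5% rate: 16–40 of 800 patients, and power between 77.9% and 81.4% against 82.1%, depending on the rate and on whether those patients are lost or kept without drug effect. The case for change is that these withdrawals are avoidable with a test already planned.

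**What to change.** 1. In Selection and Withdrawal of Subjects, extend the diabetes exclusion to a baseline HbA1c in the laboratory's diabetic range.
2. In Method of Assigning Subject Identification, replace the undefined term with a stated order: consent, baseline bloods, documented review of HbA1c, eGFR and bilirubin against the exclusion criteria, then the random number. Patients who fail are screen failures and are not randomised.
3. Reconcile the stopping rule in Trial Design, the withdrawal rule in Assessment of Safety and the intention-to-treat statement in Outcomes and Assessment of Efficacy. Say whether the rhythm outcome is still collected, and analysed in the assigned arm, for a patient who meets an exclusion after randomisation. This is needed even with a baseline screen, because diabetes may be diagnosed later from the follow-up HbA1c.

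Cost: protocol wording, a few screen failures, a short delay before allocation and a slightly narrower population. The three results are already on the baseline list, so no new test is needed for them. Serum bicarbonate is also an exclusion but is on neither baseline list; if the review is to cover every laboratory criterion, the protocol must say where that value comes from.

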### **Treatment of Subjects:**

At baseline all study patients will be assessed for:

Age, Gender, Weight, BMI, Tobacco Use, Hypertension, Hemoglobin A1c, Hyperlipidemia, serum CRP, eGFR, liver function tests (AST, ALT, ALP, bilirubin, albumin, INR), History of Coronary Artery Disease by MI, PCI, or CABG, History of Valvular Disease, History of Sleep Apnea, Type of AF and duration, Number of Antiarrhythmic Medications (not including beta-blockers or calcium channel blockers).

In addition, patients will fill out a survey to determine their Atrial Fibrillation Severity Score (AFSS) – a validated tool to assess the symptomatic burden of AF - and will receive education on dietary changes and exercise.

Subjects will be randomized to receive either Metformin (500 mg tablet) or into the control group. Subjects will be instructed to take one tablet twice a day with meals. Over a 3 week period, the dosage will be increased to 2000 mg daily (given in a divided dose of 1000 mg twice a day) as tolerated by the patient.

Patients will be followed up in regular intervals after the initial attempt at rhythm control. The minimum follow up interval is every three months. More frequent follow up may be scheduled as deemed necessary by the treating physician.

At the time of the first attempt at rhythm control, at the 3 month follow up, and at the 6 month follow up all study patients will be assessed again for:

Weight, BMI, Hemoglobin A1c, serum CRP, eGFR, liver function tests (AST, ALT, ALP, bilirubin, albumin, INR), number of antiarrhythmic agents, presence of AF by EKG, Atrial Fibrillation Severity Score, occurrence of adverse events.

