#### **Storage and Dispensing:**

The study drug is commercially available. Study drug will be stored in accordance with the package insert at  $20^{\circ}-25^{\circ}$  C ( $68^{\circ}-77^{\circ}$  F); excursions permitted to  $15^{\circ}-30^{\circ}$  C ( $59^{\circ}-86^{\circ}$  F).

Investigational product documentation will be maintained that includes all processes required to ensure drug is accurately administered. This includes documentation of drug storage, administration and storage temperatures.

Per package insert: The usual starting dose of GLUCOPHAGE® Tablets is 500 mg twice a day or 850 mg once a day, given with meals. Dosage increases should be made in increments of 500 mg weekly or 850 mg every 2 weeks, up to a total of 2000 mg per day, given in divided doses.

In this study the starting dose will be 500 mg daily, given with meals. Over a 3 week period, the dosage will be increased to 2000 mg daily (given in a divided dose of 1000 mg twice a day) as tolerated by the patient, according to the schedule below.

Figure 2.

Study Drug	Week 1	Week 2	Week 3	Week 4
Number of pills in Morning	1	1	2	2
Number of pills in Evening	0	1	1	2
Total pills per day	1	2	3	4
Daily dose (of 500 mg tablet)	500 mg	1000 mg	1500 mg	2000mg

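### The protocol gives two different starting doses of metformin: 500 mg a day in two sections, 1000 mg a day in a third

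*Combined protocol and SAP*

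**What the plan says.** Three sections of the combined protocol and SAP describe how metformin is started.

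- **Trial Design:** "Metformin will be initiated at 500 mg daily and increased as tolerated to 2000 mg daily over a three week period". A designee oversees initiation and the increases; the specific duty stated is that of a person "who will be responsible for stopping dosage increases if side effects occur".
- **Storage and Dispensing:** after citing the package insert's usual starting doses, the text turns to this trial: "In this study the starting dose will be 500 mg daily, given with meals". The increase to 2000 mg a day is to proceed "as tolerated by the patient, according to the schedule below", meaning the Figure 2 table. In Week 1 of that table the morning count is 1 and the row "Number of pills in Evening" shows 0, for a daily dose of 500 mg.
- **Treatment of Subjects:** "Subjects will be randomized to receive either Metformin (500 mg tablet) or into the control group". Then: "Subjects will be instructed to take one tablet twice a day with meals". The next sentence begins: "Over a 3 week period, the dosage will be increased to 2000 mg daily". This section does not refer to Figure 2 and lists no steps of its own.

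**The concern.** Treatment of Subjects tells staff what to instruct subjects to do, and that instruction conflicts with the other two sections. The twice-daily sentence comes directly after randomization and directly before the escalation, so it reads as the level from which the dose rises. It mentions no once-daily first step.

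Staff working from different sections would give different initial doses, and whichever start is used departs from some part of the protocol. Potential Risks describes metformin's gastrointestinal effects as dose dependent, so the point bears on tolerability as well as consistency. Study Drug Compliance requires drug accountability at each visit, and the tablet count to expect during titration depends on which start was used.

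**Working it through.** **Inputs.** Tablet strength is 500 mg (Treatment of Subjects; Figure 2). Tablet counts come from Figure 2 and from the twice-daily instruction. The metformin group has 400 patients (Statistics). Daily dose = tablets per day × 500 mg.

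**Figure 2 reproduced.** The table is internally correct in every week:

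| Week | Morning + evening | Tablets × 500 mg | Dose in table |
|---|---|---|---|
| 1 | 1 + 0 = 1 | 500 mg | 500 mg |
| 2 | 1 + 1 = 2 | 1000 mg | 1000 mg |
| 3 | 2 + 1 = 3 | 1500 mg | 1500 mg |
| 4 | 2 + 2 = 4 | 2000 mg | 2000 mg |

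**The two starts compared.**

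| | Trial Design; Storage and Dispensing | Treatment of Subjects |
|---|---|---|
| First day | 1 × 500 = 500 mg | 2 × 500 = 1000 mg |
| First seven days, tablets | 7 × 1 = 7 | 7 × 2 = 14 |
| First seven days, dose | 7 × 500 = 3,500 mg | 14 × 500 = 7,000 mg |
| Rise still needed to reach 2000 mg a day | 2000 − 500 = 1500 mg | 2000 − 1000 = 1000 mg |

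The ratio of initial doses is 1000 / 500 = 2. The seven-day difference is 14 − 7 = 7 tablets, or 7,000 − 3,500 = 3,500 mg per patient. The seven-day figure for Treatment of Subjects assumes no increase within the first week, because that section gives no step dates. The first-day figure needs no such assumption.

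**Could the twice-daily instruction be a later step?** It equals the Week 2 dose in Figure 2. Reading it as Week 2, however, requires a preceding once-daily week that Treatment of Subjects does not contain. That section also repeats the escalation sentence from Storage and Dispensing without the closing reference to the schedule, so it does not send the reader to the table.

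**The case against.** The best defence accepts the conflict and disputes its weight.

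- **Label context.** Storage and Dispensing cites 500 mg twice a day as one of the package insert's usual starting doses, so the higher figure matches a start the protocol itself quotes. This stands, and it tempers the safety concern. It does not reconcile the sections, because the same paragraph expressly sets the study's start apart from the label's.
- **Only one complete schedule exists.** Figure 2 is the only week-by-week version, Trial Design agrees with its first step, and Treatment of Subjects never calls its dose a starting dose. This makes two working schedules less likely, but it is not a rule of precedence.
- **Local oversight.** One hospital, one outpatient pharmacy and a designee are involved, so divergent dosing is possible rather than demonstrated. That is fair. Still, the designee's specific stated duty is to halt increases when side effects occur, which does not settle the first dose.
- **Short duration.** If the twice-daily dose is simply held, Figure 2 reaches the same daily dose in Week 2. The gap then lasts about one week, early in a six-week run-in, whereas outcomes are assessed 3 and 6 months after the rhythm-control attempt. This stands as a limit on the consequences.

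None of these removes the contradiction on the first day.

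**Conclusion.** The concern holds. The protocol gives two initial doses that differ by a factor of 2 (500 versus 1000 mg a day), and the current text does not reconcile them. Over a first week with no increase the difference is 3,500 mg per patient, for up to 400 patients.

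The conflict is confined to titration: the sections agree on the 2000 mg daily target and the three-week period, and ablation at six weeks is not in dispute. The documents give no rates of gastrointestinal effects at the two doses. No harm, and no effect on the primary result or the sample size, is shown. The correction is required because a direct dosing instruction for the investigational drug contradicts the dosing schedule, so the protocol cannot be followed as written on day 1.

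**What to change.** Reconcile Trial Design, Storage and Dispensing (text and Figure 2) and Treatment of Subjects so that a single titration schedule, with all its steps, applies throughout. Treatment of Subjects should either state that schedule in full or refer to the table. Then check that the instructions given to subjects and the dispensing records agree with it. Which schedule applies is for the sponsor to decide; this review takes no view.

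The cost is a change of protocol wording plus that check. Sample size, endpoints and analysis are unaffected.

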#### **Study Drug Compliance:**

Study drug dispensed to the subjects will be tracked. Subjects will return empty study drug containers and unused study drug at those visits when a new supply of study drug is to be received. Study drug accountability will be performed at each visit. Subjects should report any unintentional interruption or missed doses of 7 consecutive days or more to the study-site personnel at each visit. It is understood that subjects may occasionally miss a dose or that a subject may be placed on temporary discontinuation.

#### **Outcomes and Assessment of Efficacy:**

The primary outcome by intention to treat analysis will be maintenance of sinus rhythm by chart review, EKG, and Atrial Fibrillation Severity Score at 3 and 6 months after the initial attempt at rhythm control.

Secondary outcomes will include hospitalization related to arrhythmic events or medication side effects, number of antiarrhythmic medications, number of repeat ablations, BMI, Hemoglobin A1c, and number of thromboembolic events.

Pre-specified subgroup comparisons will include comparing patients randomized to metformin who have a 5% reduction in weight at 6 months to all control patients who achieve a 5% reduction in weight, and to all control patients.

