### **Trial Objective and Purpose:**

The purpose of this trial is to determine if the upstream use of metformin in patients with atrial fibrillation and obesity undergoing a rhythm control strategy will increase the frequency of maintenance of sinus rhythm at six months. The primary endpoint is the number of patients in normal sinus rhythm after six months of follow up. Secondary endpoints are amount of weight loss, change in BMI, change in hemoglobin A1c, number of thromboembolic events, and burden of atrial fibrillation based on the Atrial Fibrillation Severity Score (AFSS).

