Patients will be followed up in regular intervals after the initial attempt at rhythm control. The minimum follow up interval is every three months. More frequent follow up may be scheduled as deemed necessary by the treating physician.

[figure not shown]
At the time of the first attempt at rhythm control, at the 3 month follow up, and at the 6 month follow up all study patients will be assessed again for:

Weight, BMI, Hemoglobin A1c, serum CRP, eGFR, liver function tests (AST, ALT, ALP, bilirubin, albumin, INR), B12, lactic acid, number of antiarrhythmic agents, presence of AF by EKG, and Atrial Fibrillation Severity Score.

At each 3-month and 6-month follow up, data will be reviewed by a designee who will use the criteria described below for reporting to the Medical Monitor. The patient will also be assessed for the occurrence of any adverse events as defined below and adverse events will be reported to the medical monitor.

At the end of 6 months of therapy, the decision to continue Metformin beyond 6 months will be made in conjunction with the patient's treating cardiologist and primary care physician.

Figure 1.

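### The primary outcome is defined in two ways that differ in time point and in the role of the AFSS symptom survey, and the 30% recurrence assumption is tied to neither

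*Combined protocol and SAP*

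**What the plan says.** Trial Objective and Purpose states: "The primary endpoint is the number of patients in normal sinus rhythm after six months of follow up". It gives no method of ascertainment. The purpose sentence just before it asks whether metformin "will increase the frequency of maintenance of sinus rhythm at six months". The secondary endpoints in that section include "burden of atrial fibrillation based on the Atrial Fibrillation Severity Score (AFSS").

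Outcomes and Assessment of Efficacy gives the primary outcome, by intention to treat, as "maintenance of sinus rhythm by chart review, EKG, and Atrial Fibrillation Severity Score at 3 and 6 months", counted from the first attempt at rhythm control. AFSS is absent from the secondary list there.

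Trial Design calls AFSS "a validated tool to assess the symptomatic burden of AF" and says that the study adds "EKGs for measuring outcomes in both the intervention and control groups". The follow-up lists keep the two measures apart: "presence of AF by EKG, and Atrial Fibrillation Severity Score" in Trial Design and "presence of AF by EKG, Atrial Fibrillation Severity Score, occurrence of adverse events" in Treatment of Subjects.

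Statistics assumes 30% recurrence of AF after ablation and 30% less on metformin, with 80% power, two-sided testing at .05, up to 3% attrition and 400 per arm. It gives no time point, no method of ascertainment and no reference to either definition.

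**The concern.** The two sections can classify the same patient differently, and an analyst following the protocol cannot tell which governs. Three things are left open: whether month 3 counts; how chart review, EKG and AFSS combine when they disagree; and what AFSS result would mean loss of sinus rhythm. A primary outcome left open in this way could be settled after the data are seen, in a trial of 800 patients with an estimated five years of accrual.

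AFSS is the more serious part. It is a patient-completed survey of symptoms, and the control group is described without placebo or blinding. Patients who know their assignment could report symptoms differently, and that difference would enter a rhythm endpoint directly. The documents give no basis for estimating its size.

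The planning rate of 30% also cannot be checked against an endpoint, because it is not attached to one.

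**Working it through.** **Step 1: the two definitions side by side.**

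| Feature | Trial Objective and Purpose | Outcomes and Assessment of Efficacy |
|---|---|---|
| Time point | six months | 3 and 6 months |
| Time origin | not stated | first attempt at rhythm control |
| Ascertainment | not stated | chart review, EKG, AFSS |
| AFSS | secondary | part of primary; not in secondary list |

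The differences that matter are the time points and the role of AFSS. Chart review and EKG are additions, because the first section names no method.

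**Step 2: a test case.** Take a patient in AF at month 3 and in sinus rhythm at month 6. Under Trial Objective and Purpose this is a success. Under Outcomes there are two readings:
- Sinus rhythm is required at both visits: failure.
- The visits are separate assessments: failure at month 3 and success at month 6, with no statement of which is primary or how two tests would be handled.

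**Step 3: reproduce the stated sample size.** Inputs from Statistics: p1 = 0.30; p2 = 0.30 × 0.70 = 0.21; two-sided alpha .05 (z = 1.960); power 80% (z = 0.842). The mean rate is 0.255.

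n = [1.960 √(2 × 0.255 × 0.745) + 0.842 √(0.30 × 0.70 + 0.21 × 0.79)]² / 0.09² = (1.208 + 0.516)² / 0.0081 = 367 per arm.

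With continuity correction: (n/4) × [1 + √(1 + 4/(n × 0.09))]² = 389. Then 389 / 0.97 = 401, against the stated 400. The uncorrected figure gives 367 / 0.97, about 379, so the corrected formula is the one that matches. The arithmetic is sound.

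**Step 4: does the choice of definition matter to power?** Evaluable patients per arm: 400 × 0.97 = 388. Uncorrected power is Φ{[(p1 − p2) √388 − 1.960 √(2 × mean × (1 − mean))] / √(p1(1 − p1) + p2(1 − p2))}. At 30% against 21% this is Φ[(1.773 − 1.208) / 0.613] = Φ(0.921) = 82%.

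Every other rate below is an assumption, for illustration only.

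| Assumption | Control vs metformin | Power |
|---|---|---|
| Planned | 30% vs 21% | 82% |
| Lower rate, relative reduction fixed at 30% | 25% vs 17.5% | 72% |
| Lower rate, relative reduction fixed at 30% | 20% vs 14% | 60% |
| 5 points fewer failures in both arms | 25% vs 16% | 88% |
| 5 points more failures in both arms | 35% vs 26% | 78% |

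At a control rate of 25%, power is 72% or 88% depending only on what is assumed about the treatment effect. The definition therefore matters, but the sign of the change does not follow from the event rate alone.

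**Step 5: AFSS misclassification (assumed).** If 5% of patients truly in sinus rhythm in each arm were labelled recurrences, the rates become 0.30 + 0.05 × 0.70 = 33.5% and 0.21 + 0.05 × 0.79 = 25.0%, and power is 75%. Here the control rate rises while power falls. This shows dilution from equal error in both arms; reporting bias that differs by arm is a separate matter and cannot be sized.

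**The case against.** The Outcomes wording may be no more than a list of sources and visits for the single aim in Trial Objective and Purpose, whose purpose sentence also speaks of maintaining sinus rhythm. That is a fair reading, and it makes the difference in concept smaller than the difference in timing. It does not settle the matter: no passage says so, and it leaves unexplained why AFSS moves from a secondary endpoint into the primary one.

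A reader might go further and infer that the month-6 definition must have the lower failure rate and therefore the lower power. AFSS and chart review aside, the first half holds if the other definition requires sinus rhythm at both visits, since failures at month 6 are then a subset of failures at either visit. The second half does not hold. It needs the same relative reduction under both definitions, and Statistics gives that reduction once without attaching it to an endpoint. With an equal shift in both arms the direction reverses, as Step 4 shows. For the same reason, no break-even number of patients should be quoted.

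A reader might also take a single month-6 EKG, ignoring everything before it, as the only correct endpoint. The documents do not support that. It would drop the planned chart review and fit poorly with the words maintenance and recurrence. It is one defensible choice, and the sponsor should make the choice explicitly.

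**Conclusion.** The point stands, and it must be fixed before outcome data are seen. The two sections give different primary outcomes, in time point and in the role of AFSS, and nothing reconciles them. Using AFSS to classify rhythm exposes the primary outcome to reporting bias whose size is unknown.

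The documents do not show that the sample size is wrong or that the trial is underpowered. The 400 per arm reproduces from the plan's own inputs. What is missing is a link between the 30% and an endpoint. The Background figure of a 70-80% decrease in AF frequency after ablation may be its origin, but the protocol does not say so, and that figure has no patient-level definition or time point either. The illustrative power range of 60% to 88% rests on assumed rates and assumed treatment effects; it shows that the choice of definition matters, not which way it would move power.

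**What to change.** - State one binary primary endpoint, worded identically in Trial Objective and Purpose and in Outcomes and Assessment of Efficacy, and tested once. Make month 6 after the initial ablation the primary time point, with rhythm documented by EKG. This keeps the six-month aim of the first section and the time origin of the second.
- Take AFSS out of the primary outcome and list it as secondary in both sections.
- State, before any outcome data are seen, whether AF documented at month 3, or by chart review before month 6, counts as failure. Report the alternative definition as a pre-specified sensitivity analysis.
- In Statistics, say that 30% against 21% refers to the chosen endpoint, or restate the power for the rates expected under it. Say whether a continuity correction is used.

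The cost is a protocol amendment with IRB approval, and possibly a less favourable stated power. The 3- and 6-month EKGs and AFSS are already in the visit lists in Trial Design and Treatment of Subjects. Chart review is already planned, though only Outcomes and Assessment of Efficacy mentions it.
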